7.8 Completion of Study

Patients will be considered to have completed the study if they (1) have received at least 1 cycle of treatment, AND (2) experienced progressive disease OR (3) experienced unacceptable toxicity. In the absence of progressive disease or unacceptable toxicity, and in the setting of continued clinical benefit, patients may be permitted to remain on therapy upon discussion with the PI. Patients wishing to continue therapy beyond cycle 12 may continue on their current therapy at the discretion of their treating provider. Patients receiving enzalutamide will no longer receive this as a study medication beyond the 12-month timepoint but may be able to obtain the medication through standard prescribing methods.

Withdrawal of Patients from Study

Patients will be informed that they have the right to withdraw from study treatment at any time for any reason, without prejudice to their medical care. A patient may be withdrawn from study treatment for any of the following reasons:

- Adverse Event
- Protocol Violation
- Radiographic Progressive Disease as defined in section 7.2
- Serologic progressive disease as defined in section 7.2
- Symptomatic Deterioration
- Study Terminated by the University of Colorado Cancer Center
- Withdrawal by Subject
- Lost to Follow-up
- Other

At the time of study drug discontinuation, all study procedures outlined for the EOS visit should be completed within 30 days after the last dose of study drug. The primary reason for a patient's withdrawal from the study is to be recorded.

The consequence of withdrawal of consent by a patient will be that no new information will be collected from that patient and added to the existing data or any database. However, every effort will be made to follow all patients for safety.

7.9 Study Compliance

Study drug will be dispensed only to eligible patients under the supervision of the investigator or identified sub-investigator(s). The appropriate study personnel will maintain records of study drug receipt and dispensing, including the following: applicable lot numbers and total drug administered in milligrams. Any discrepancy regarding the dose administered and the reason for the discrepancy will be noted.

Patients will receive a sufficient quantity of enzalutamide for each treatment cycle. The study center staff will check the returned pill bottles at each study visit to ensure proper compliance with dosing. Patients who are not compliant with the dosing schedule may be withdrawn from the study.

8. INVESTIGATIONAL AGENTS

8.1 Precautions and Restrictions

Patients should be instructed to consult with the investigator before taking any new medications, including over-the-counter and herbal products. Patients should be instructed to limit the use of alcohol while enrolled in this study.

8.2 Description of Investigational Agents

8.2.1 Enzalutamide

Enzalutamide 40 mg capsules are white to off-white oblong soft gelatin capsules imprinted in black ink with MDV. Enzalutamide is provided as liquid-filled soft gelatin capsules for oral administration. Each capsule contains 40 mg of enzalutamide as a solution in caprylocaproyl polyoxylglycerides. The inactive ingredients are caprylocaproyl polyoxylglycerides, butylated hydroxyanisole, butylated hydroxytoluene, gelatin, sorbitol sorbitan solution, glycerin, purified water, titanium dioxide, and black iron oxide. Enzalutamide is an androgen receptor inhibitor. The chemical name is 4-{3-4-cyano-3-(trifluoromethyl) phenyl-5, 5-dimethyl-4-oxo-2-sulfanylideneimidazolidin-1-yl-2-fluoro-N-methylbenzamide. Enzalutamide is a white crystalline non-hygroscopic solid. It is practically insoluble in water.

8.2.2 Androgen deprivation therapy

ADT includes agents such as degarelix, goserelin, leuprolide, triptorelin, and histerelin. These agents are long-acting analogues of the GnRH peptide and alter the feedback loop of FSH and LH production to subsequently reduce circulating testosterone levels. These agents are FDA approved and may be used for the purposes of ADT in this study. These agents are generally administered as a subcutaneous or intramuscular injection and should be administered according to manufacturer instruction. Please refer to the FDA package insert for information.

8.3 Preparation, Reconstitution, and Dispensation

The University of Colorado Cancer Center clinical trials team and the PI will assign each patient who signs a consent form a patient number. Patients will be dispensed bottles of study drug containing an appropriate number of capsules in order to achieve the assigned doses. Patients may be dispensed a maximum of 3 complete cycle's capsules.

Patients will be asked to bring back all remaining study drug at each visit. All unused study drug and the amount of study drug returned will be recorded on the drug accountability form. Patients will be instructed to store the enzalutamide capsules only in the bottles dispensed.

8.4 Storage, Handling, Accountability

8.4.1 Enzalutamide

Enzalutamide capsules are available in bottles of 120 capsules. These should be stored at 20°Celsius (C) to 25°C in a dry place with the container tightly closed.

8.4.2 Handling and Accountability

All clinical drug supplies must be kept in an appropriate, limited-access, secure place until used or destroyed. The investigator must maintain 100% accountability for all study medication received and dispensed. Proper drug accountability includes, but is not limited to:

- Frequently verifying that actual inventory matches documented inventory
- Verifying that the log is completed for the drug lot used to prepare each dose
- Verifying that all containers used are documented accurately on the log
- Verifying that required fields are completed accurately and legibly

If any dispensing errors or discrepancies are discovered, the PI must be notified immediately.

The investigator must maintain a current inventory of all study medication delivered to the site, inventory at the site, and records of patient use. This log must accurately reflect the drug accountability of the study medication at all times. The following information will be recorded at a minimum: protocol number and title, name of investigator, site identifier and number, description of study medication, expiration date, date and amount dispensed, and the date and amount returned to the site by the patient, including the initials of the person dispensing and receiving the study medication. The log should include all required information as a separate entry for each patient to whom study medication is dispensed.

Before site closure, or at appropriate intervals, a representative from the PI or its designee will perform clinical study material accountability and reconciliation before clinical study materials are destroyed. The investigator will retain the original documentation regarding clinical study material accountability and destruction.

The investigator will monitor any expiration date and subsequently segregate and destroy expired clinical study drug.

9. STUDY CONDUCT

This trial will be conducted in compliance with the protocol, good clinical practice (GCP), applicable regulatory requirements, and International Conference on Harmonisation (ICH) guidelines.

9.1 Oversight of multiple participating sites

Study will be conducted at multiple sites with the University of Colorado Anschutz Campus as the coordinating site. [name], as the Lead PI, will work with the Site PI(s) to insure proper training and conduct.

A PI oversight plan has been drafted to outline the procedures for maintaining oversight, data monitoring and study auditing. All study sites involved will follow the process outlined in the document in order to ensure safe and accurate conduct.

9.2 Arrangements for Recruitment of Patients

Recruitment and enrollment strategies for this study may include recruitment from the investigator's local practice or referrals from other physicians. If advertisements become part of the recruitment strategy, they will be reviewed by the institutional review board (IRB)/independent ethics committee

(IEC). It is not envisioned that prisoners (or other populations that might be subject to coercion or exploitation) will be enrolled into this study.

The study will aim to enroll at least 1 patient per month to the trial.

9.3 Treatment Group Assignments

Patients will be assigned through the randomization process with a 1:1 ratio of patients in each treatment group. Randomization will occur centrally through a non-clinical project manager at the coordinating site. Participating sites will contact this central manager for randomization assignment during regular business hours (M-F 8-5pm).

10. STATISTICAL AND QUANTITATIVE ANALYSES

10.1 Statistical Methods

We estimate a 7% (2 patients) and 32% (9 patients) incidence of metabolic syndrome for enzalutamide and ADT treated patients based on historic data ⁷. Historical cross-sectional data would suggest that almost 50% of patients on ADT will develop metabolic syndrome, however, the trial population proposed will be pre-selected. Twenty-eight (28) patients in each of the two groups will provide 80% power to detect the 25% difference using a one-sided chi-square test with a significance level of 0.05 (actual alpha=0.054).

10.1.1 Endpoint Analysis

Primary endpoint

Metabolic syndrome incidence will be summarized by the proportion of patients with at least 3 of the 5 pre-specified criteria within the first 12 months of therapy.

Secondary endpoint

The secondary endpoints will be presented as follows:

Metabolic syndrome incidence will be summarized by the proportion of patients acquiring with at least 3 of the 5 pre-specified criteria within the first 6 months of therapy.

The change in bone turnover markers from baseline will be assessed for each treatment group. Measurements will be taken at day 1 of each cycle and reported as a continuous variable. A paired t-test will test within an arm as to whether the change from baseline to each time point is significantly different from zero.

The change in bone density, free fat mass, and fat mass will be measured at baseline, 3 months and 12 months and assessed for each treatment group. A paired t-test will test within an arm as to whether the change from baseline to each time point is significantly different from zero.

The change in QOL scores as measured by the FACT-P and SHIM at each visit, will be assessed in each treatment group.

Median time to PSA progression as defined in section 7.2. Time to PSA progression is defined as the time from randomization to the earliest objective evidence of PSA progression as defined per

protocol. If a patient has had a decline in PSA while on study, the PSA progression date is defined as the time from documented PSA nadir to an increase in PSA with confirmation as defined by protocol. Time to radiographic progression is defined as the time from randomization to the earliest objective evidence of radiographic progression as defined per protocol. Patients will be monitored at regular intervals for PSA change and radiographic change. Log rank test will be used to compare the distributions of above variables between the group treated with enzalutamide to the group on standard ADT.

The change in markers of inflammation as measured by circulating hs-CRP will be obtained at the beginning of each cycle.

Adverse events data will be summarized using tables and descriptive statistics.

The change in SPPB from baseline to 12 months will be measured as a continuous outcome. A clinically relevant change is a change in total score of 1, with a standard deviation at baseline of 1.5⁴².

Mean, standard deviation, median, and range will be reported for each outcome at each time point, and the mean and standard deviation of the changes, will be calculated. One-group t-test will be used to estimate effect size of each outcome measure and test if the change is significant at 0.05 significance level. Pearson or Spearman correlation coefficients will be used to assess the association between continuous variables.

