1.4 Rationale for study design

Improved understanding of the biology of prostate cancer has allowed for the development of agents, which more effectively manipulate the androgen axis even under castrate conditions. Not only reduction in circulating testosterone, but also improved blockade of the androgen receptor has led to an improvement in survival for patients with metastatic castrate resistant prostate cancer (CRPC). The development of a new generation of agents, such as enzalutamide, that preserve circulating testosterone levels while acting on the androgen receptor, provide new therapeutic opportunities for an active single agent with the potential for a reduction of the long term effects associated with ADT. Single agent data of enzalutamide reveals an excellent PSA response and tolerance profile²⁸. Preservation of these hormone levels may delay the adverse effects associated with long term ADT that contribute to development of metabolic syndrome.

The influence of the adverse events associated with newer agents on a patient's QOL is increasingly used to guide cancer care²⁹, and understanding the comparative effectiveness of agents is important. Men with prostate cancer have higher rates of noncancerous mortality than men in the general population, perhaps due to the contribution of the hypogonadal state in worsening common causes of death such as heart disease and diabetes. The clustering of cardiovascular risk factors, which occurs with ADT, may not be found in patients treated with enzalutamide due to its preservation of systemic testosterone levels. There has not been a longitudinal analysis of the development of metabolic syndrome in patients on ADT, nor a structured evaluation of the development of metabolic syndrome, or metabolic changes in patients treated with enzalutamide. This protocol will evaluate the effect of androgen blockade via enzalutamide versus traditional ADT on development of metabolic syndrome, changes in body composition, changes in quality of life, and changes in physical function in patients with advanced prostate cancer.

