2.2 Secondary Objectives

In patients treated with enzalutamide versus traditional ADT:

- To determine the incidence of metabolic syndrome within 6 months, as defined by the Adult Treatment Panel III, in patients treated with enzalutamide compared to standard androgen deprivation therapy
- To assess bone health, as measured by a DXA scanner
- To assess body composition (sarcopenic obesity), as measured by measurements of fat on CT
- To assess QOL, as measured by the FACT-P and SHIM
- To assess time to PSA progression and time to radiographic progression. Progression will be defined as lack of clinical benefit in the setting of either rising PSA, growth of visceral or soft tissue metastasis, or development of new bone metastasis as defined per protocol
- To assess the incidence of developing individual risk factors, or components, which comprise metabolic syndrome
- To assess the change in hs-CRP as a marker of inflammation
- To assess the safety and tolerance of enzalutamide or ADT
- To assess the change in physical function as measured by the Short Physical Performance Battery (SPPB)

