3.2 Secondary Endpoints

- Incidence of metabolic syndrome within 6 months, as defined by the ATP III, in patients treated with enzalutamide versus patients treated with standard testosterone-lowering ADT
- Change in bone density, as measured by a DXA scanner
- Change in bone turnover as measured by bone-specific alkaline phosphatase and N-telopeptide
- Change in body composition (fat distribution as measured on CT)
- Change in QOL, as measured by the FACT-P and SHIM
- Time to PSA progression and time to radiographic progression. Progression will be defined as lack of clinical benefit in the setting of either rising PSA, growth of visceral or soft tissue metastasis, or development of new bone metastasis as defined per protocol
- Incidence of developing individual risk factors, or components, which comprise metabolic syndrome
- Change in inflammatory markers as measured by serum hs-CRP

- Safety and tolerability as assessed by regular recording of toxicities via physical exam and laboratory analysis using the CTCAE v4.1 guidelines
- Change in physical function as measured by the Short Physical Performance Battery

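### Section 10.1.1 plans no between-arm estimate, interval or test for any continuous secondary endpoint, although the secondary objectives compare enzalutamide with ADT

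*Combined protocol and SAP*

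**What the plan says.** The aim is comparative. Section 2.2 introduces the whole list of secondary objectives with "In patients treated with enzalutamide versus traditional ADT", and section 1.4 says "This protocol will evaluate the effect of androgen blockade via enzalutamide versus traditional ADT on development of metabolic syndrome, changes in body composition", going on to name quality of life and physical function. Section 4.1 randomizes 56 patients 1:1, stratified by metastasis.

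The analysis in section 10.1.1 is not comparative for the continuous endpoints:

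- **Bone turnover markers, bone density, free fat mass, fat mass:** "A paired t-test will test within an arm as to whether the change from baseline to each time point is significantly different from zero".
- **hs-CRP:** "The change in markers of inflammation as measured by circulating hs-CRP will be obtained at the beginning of each cycle". No analysis is named.
- **SPPB:** "The change in SPPB from baseline to 12 months will be measured as a continuous outcome". A 1-point change is called relevant and a baseline SD of 1.5 is given, but no contrast is named.
- **FACT-P and SHIM:** change is to be assessed in each group. Section 7.4 says both instruments are used descriptively.
- **All outcomes (closing paragraph):** summary statistics, then "One-group t-test will be used to estimate effect size of each outcome measure and test if the change is significant", at the 0.05 level. The text does not say whether this is run per arm or on both arms pooled, or whether it is one- or two-sided.

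The only between-arm method in section 10.1.1 is "Log rank test will be used to compare the distributions of above variables between the group treated with enzalutamide" and the ADT group. It directly follows the definitions of time to PSA progression and time to radiographic progression.

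**The concern.** A test of change against zero in one arm does not use the other arm, so it gives up the comparison that randomization supports. If only the stated tests are reported, the reader gets up to two p-values per endpoint and visit and no estimate of the treatment difference. Two misreadings then come easily: that the arms differ because one p-value is below 0.05 and the other is not, or that they are alike because both are below 0.05. Neither follows.

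The means and SDs of change would let someone compute a difference later. The estimator, the covariates, the visit and the handling of patients without month-12 data would then be chosen after the data are seen.

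**Working it through.** **Is a between-arm method planned anywhere?** The log-rank test in section 10.1.1 refers loosely to the variables above it, but it compares times to event and cannot be applied to change scores. Apart from that sentence, neither section 10 nor the rest of the protocol gives a two-sample test, ANCOVA, mixed model, mean difference or between-arm interval for a continuous endpoint.

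**The plan's own figures.** No power or precision is stated for any continuous secondary comparison. The one power statement, for the primary endpoint in section 10.1, reproduces. An exact enumeration of the uncorrected one-sided chi-square test with 28 per arm at 7% versus 32% gives power 0.81 and actual alpha 0.054, against the stated 80% and 0.054. This concern does not touch it.

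**How often would the within-arm tests mislead?** Let both arms have the same true change, d in units of the SD of change, and let p be the power of a one-sample t-test (noncentral t, two-sided 0.05). The arms are independent, so

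P(exactly one arm significant) = 2p(1 − p).

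Inputs: 28 per arm (section 10.1). The values of d, two-sided testing and 24 evaluable per arm (4/28 = 14% loss) are assumptions, because the documents give no SD of change and no dropout rate. Results below use unrounded p.

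| d | p, n=28 | 2p(1−p) | p, n=24 | 2p(1−p) |
|---|---|---|---|---|
| 0.20 | 0.175 | 0.289 | 0.156 | 0.263 |
| 0.38 | 0.492 | 0.500 | 0.430 | 0.490 |
| 0.55 | 0.801 | 0.319 | 0.733 | 0.392 |
| 0.80 | 0.983 | 0.034 | 0.963 | 0.071 |
| 1.00 | 0.999 | 0.002 | 0.997 | 0.006 |

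**The same for SPPB.** Inputs: a common 1-point change and baseline SD 1.5 (section 10.1.1). Assumed: the same SD at follow-up, and correlation r between baseline and follow-up. Then SD of change = 1.5 × √(2(1 − r)) and d = 1/SD.

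| r | SD of change | d | p, n=28 | 2p(1−p) | p, n=24 | 2p(1−p) |
|---|---|---|---|---|---|---|
| 0.3 | 1.775 | 0.563 | 0.820 | 0.296 | 0.753 | 0.372 |
| 0.5 | 1.500 | 0.667 | 0.925 | 0.139 | 0.878 | 0.214 |
| 0.7 | 1.162 | 0.861 | 0.992 | 0.015 | 0.981 | 0.037 |

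A simulation of 40,000 trials per cell agrees: 0.297, 0.138 and 0.015 with 28 per arm; 0.370, 0.215 and 0.037 with 24.

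**What would the missing estimate deliver?** For an SPPB difference adjusted for baseline and stratum, the 95% CI half-width is

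t(0.975, 2n − 4) × 1.5 × √(1 − r²) × √(2/n).

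At r = 0.5 and n = 28 this is 2.007 × 1.5 × 0.866 × 0.267 = 0.70. At r = 0.3, 0.5 and 0.7 the half-widths are 0.77, 0.70 and 0.57 points with 28 per arm, and 0.83, 0.76 and 0.62 with 24. An unadjusted comparison of changes at SD of change 1.5 (r = 0.5) has half-width 0.80 and power 0.69 for a 1-point difference with 28 per arm.

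**The case against.** The strongest reply is that these endpoints may be meant as descriptive. Section 3.2 names the ADT comparator for metabolic syndrome but words the continuous endpoints without one, for example "Change in physical function as measured by the Short Physical Performance Battery". Section 10.1.1 speaks of each treatment group and keeps the language of comparison for the log-rank endpoints. In a 56-patient phase II trial with no power for secondary endpoints, that would be a legitimate choice.

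This stands in part. For FACT-P and SHIM the descriptive use is declared, so a missing formal test there is a stated choice, although the closing paragraph then tests every outcome measure. For the other endpoints nothing declares them descriptive, sections 1.4 and 2.2 point the other way, and the plan does test at 0.05, only against zero. At best the documents leave the question open.

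Three further points are fair. Means and SDs of change, if reported by arm, would yield an unadjusted difference by arithmetic. The measurement times for SPPB (12 months) and for bone density and fat measures (3 and 12 months) are given, so what is unspecified is the between-arm contrast and the visit for it. And nowhere does the plan say it will infer a difference from one significant arm and one non-significant arm; 0.38 SD lies close to where that probability peaks. The percentages therefore show a mechanism and do not measure harm in this trial.

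**Conclusion.** The concern holds and should be fixed. Followed exactly, section 10.1.1 does not answer the comparative objectives for bone turnover, bone density, body composition, hs-CRP and SPPB. That conclusion rests on the text alone.

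The size depends on assumptions. With equal true change in both arms, the risk of a discordant pair of p-values is largest for small to moderate changes and nearly gone at 1 SD. For a common 1-point SPPB change it runs from 1.5% to 30% with 28 per arm, and from 4% to 37% with 24, over assumed correlations of 0.7 down to 0.3. In the same settings the adjusted interval has a half-width of 0.57 to 0.83 points, below the 1-point change the plan calls relevant, so the omitted estimate would be informative.

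**What to change.** For each continuous secondary endpoint meant to be comparative, state in section 10.1.1 that the main analysis is the between-arm difference at 12 months with its 95% CI, adjusted for baseline value and metastasis stratum. ANCOVA or a mixed model over the scheduled visits would serve. A mixed model also uses patients who leave before month 12, under a missing-at-random assumption. That matters because progression ends treatment (section 4.4.2) or study participation (section 7.2.2). It gains less for bone density, which has few visits. Say how an end-of-treatment assessment after early stopping is placed in time. Label these comparisons exploratory and keep within-arm changes as description.

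If an endpoint is meant to be descriptive only, say so and align section 2.2. Reconcile section 7.4 (FACT-P and SHIM descriptive) with the test of every outcome measure in section 10.1.1, and say whether that test is per arm.

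A separate point to settle in the same edit: section 10.1.1 times fat and free fat mass at baseline, 3 and 12 months, which is the DXA schedule in section 4.1. Sections 3.2 and 7.3 put body composition on CT, which section 7.2.2 schedules at baseline, 6 and 12 months. State the modality and analyse at its own times; a 12-month contrast exists under either schedule.

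The cost is SAP wording and a little analysis work. No new data are needed.

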1.2 Androgen deprivation therapy and metabolic syndrome

While many new agents have been developed for the treatment of prostate cancer, these focus on treatment in the metastatic, castrate-resistant setting. Patients requiring systemic therapy for prostate cancer continue to be initially treated with traditional gonadotropin hormone analogues, despite advances in therapeutic development. The treatment is very effective with survival results mainly impacted by disease state at initiation. The average time from biochemical recurrence, or prostate specific antigen (PSA) relapse, to development of metastatic disease is approximately 8 years² and survival for patients with metastatic disease on ADT is approximately 30 months. The median time of response for patients with biochemically relapsed disease treated with ADT is 10.8 months³. Thereafter, patients remain on ADT in combination with other therapies for the duration of their anti-cancer therapy, which may be years. Men treated with ADT experience long-term adverse effects such as fatigue, loss of muscle mass (i.e. sarcopenia), loss of bone density, increased adiposity, development of metabolic syndrome, depression, sexual dysfunction and poor quality of life (QOL)⁴⁻¹³. Men treated with ADT had lower levels of self-reported physical function and QOL in comparison to age-matched controls^{8,10,14-17}. These effects are profound for any patients but may be felt to a larger degree in the standard older patient population afflicted with prostate cancer, already dealing with the changes of decreasing functional reserve.

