7.2 Efficacy Evaluations

7.2.1 PSA

Patients will be monitored for clinical efficacy while on study. Serum PSA will be obtained every 3 months. PSA rise is allowable at the discretion of the investigator. However, patients must discontinue treatment if there is evidence of PSA progression as defined by an increase in $\geq 50\%$ from nadir and an absolute increase of at least 2 ng/mL above the nadir, occurring at least 12 weeks after start of therapy that is confirmed by two consecutive increases taken at least 2 weeks apart. The date of first recorded increase will serve as the date of progression.

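### Section 10.1.1 times PSA progression from randomization, then gives patients with a PSA decline a progression “date” that is a duration from nadir, contradicting section 7.2.1

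*Combined protocol and SAP*

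**What the plan says.** Section 10.1.1 introduces the endpoint by reference to the efficacy section: "Median time to PSA progression as defined in section 7.2". It then fixes the origin: "Time to PSA progression is defined as the time from randomization to the earliest objective evidence of PSA progression". The sentence that follows makes an exception for any patient whose PSA fell during the trial: "the PSA progression date is defined as the time from documented PSA nadir to an increase in PSA with confirmation as defined by protocol". The same paragraph gives the radiographic endpoint one origin with no exception: "Time to radiographic progression is defined as the time from randomization to the earliest objective evidence of radiographic progression". It then names the between-arm analysis: "Log rank test will be used to compare the distributions of above variables". It states no censoring rule for either endpoint.

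Section 7.2.1 uses the nadir as a level, not as a start of time. The rise must reach a stated percentage from nadir and "an absolute increase of at least 2 ng/mL above the nadir", at least 12 weeks into therapy and with confirmation. The event date is then fixed for everyone: "The date of first recorded increase will serve as the date of progression". There is no separate rule for patients whose PSA declined.

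Sections 2.2 and 3.2, and the Protocol Summary, describe progression for this endpoint in looser terms that combine loss of clinical benefit with a PSA rise or new or growing disease.

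**The concern.** A date cannot be a duration, so the exception cannot be executed as it stands. If a programmer takes it at its word and uses the nadir-to-rise interval as the patient's time, patients with a PSA decline are on a clock that starts after randomization. The median and the log-rank test would both use those times. Two programmers could obtain different results from the same data, and in an open-label trial the choice might be made after results are visible.

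The exception is not a rare case. Section 1.5 reports that 92.5% of patients in an enzalutamide monotherapy trial had an 80% PSA decline at week 25. If that held here, 0.925 × 28 = 25.9, or about 26 of 28 enzalutamide patients, would fall under the sentence. This is a floor, because the sentence is triggered by any decline. Only those who also progress would certainly be re-timed. The documents give no matching figure for the ADT arm.

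**Working it through.** The plan states no expected events, median, hazard ratio or power for PSA progression, so it has no figure of its own to reproduce.

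**Step 1. The two rules side by side.**

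| | Section 10.1.1, patients with a decline | Section 7.2.1, all patients |
|---|---|---|
| What the progression date is | an interval | a calendar date |
| Role of the nadir | start of the interval | reference level for the rise |
| Exception for decliners | yes | none |

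The general sentence in 10.1.1 agrees with 7.2.1. Only the exception conflicts.

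**Step 2. One patient.** Time on the nadir clock = (time from randomization to the rise) − (time from randomization to nadir). With nadir at 6 months and first increase at 9 months, the randomization clock gives 9 months and the nadir clock gives 9 − 6 = 3 months.

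**Step 3. The median.** Inputs from the documents: PSA at 1, 3, 6, 9 and 12 months elapsed (Table 1), no progression called before month 3 (the 12-week condition in 7.2.1), and 12 months on study. Assumptions: everyone is followed to 12 months, the nadir time is a chosen value *a*, and progression is exponential with a 10.8-month median. That figure is borrowed from section 1.2, which gives it for something narrower: "median time of response for patients with biochemically relapsed disease treated with ADT is 10.8 months". If a patient progresses before his assumed nadir, the nadir is moved to the visit before detection.

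- Proportion progressed by month t: F(t) = 1 − 2^(−t/10.8).
- F(9) = 43.9% and F(12) = 53.7%, so on the visit grid the Kaplan-Meier median from randomization is 12 months.
- On the nadir clock, patients detected at month 12 get 12 − *a*, and those detected earlier get less. The crossing moves to 12 − *a*: 11, 9 and 6 months for *a* = 1, 3 and 6.
- Censored patients sit at 12 or at 12 − *a*, never before the crossing, so re-timing them does not change this.
- A Weibull law (shape 2, same median) gives the same values: F(9) = 38.2%, F(12) = 57.5%.
- With an assumed 24-month median, F(12) = 1 − 2^(−0.5) = 29.3% (exponential) or 1 − 2^(−0.25) = 15.9% (Weibull). Half the patients never progress within 12 months, so no median is reached on either clock.

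**Step 4. The log-rank test.** Simulation: 28 per arm, identical progression in both arms, same visits, two-sided 5% test, 4,000 runs per scenario. The simulation standard error near 5% is √(0.05 × 0.95 / 4,000) = 0.34 percentage points. Assumed nadir is 3 months in one arm and 6 in the other. Only progressors are re-timed, which is what the sentence literally covers:

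| Patients who progress before the assumed nadir | Exp. 10.8 | Exp. 24 | Weibull 10.8 | Weibull 24 |
|---|---|---|---|---|
| nadir moved to the visit before detection | 5.9% | 4.5% | 7.8% | 5.6% |
| kept on the randomization clock | 5.2% | 4.5% | 6.3% | 5.7% |

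- Reference values: 4.4–5.8% on the randomization clock, and 4.4–5.8% on the nadir clock with equal nadirs.
- With nadirs varying between patients (1/3/6 against 3/6/9 months, weights 0.25/0.5/0.25): 4.8–6.7%.
- Two harsher constructions go higher: 4.7–10.2% if all progression is forced after month 6, and 5.4–17.5% if earlier progressions are moved to month 9.
- If censored patients are also timed from nadir, which the sentence does not say, the range over all constructions with nadir at 3 against 6 months is 6.7–58.7%.

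**The case against.** The best defence is that nobody would program the sentence literally. Because a date cannot be an interval, a programmer must interpret it. The paragraph names randomization as the origin and refers back to section 7.2. The natural repair is a rise measured from nadir and a clock running from randomization. That may well be what was meant. It stands as a reason to treat this as a drafting conflict rather than a deliberate choice of clock. It does not remove the conflict: the exception is in the current text, nothing reconciles it with 7.2.1, and the correction changes nothing if the benign reading was intended.

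Three stronger readings are tempting, and the documents do not support them.

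- A reader might infer that the reported median will necessarily be too short. It is shortened only if it is reached within follow-up. The sole figure available, 10.8 months, concerns ADT response in biochemical relapse, while this trial also enrols metastatic and primary-ADT patients.
- A reader might infer that the log-rank comparison is badly inflated. The sentence redefines a progression date, and a censored patient has none, so the general sentence starting at randomization is the better guide for him. On that reading the error is mostly near nominal. The large percentages need censored patients to be re-timed and nadir timing to differ between arms.
- A reader might infer a known direction of bias. The documents give no nadir times for either arm.

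**Conclusion.** The contradiction is real and should be corrected before analysis. Taken literally, the sentence takes each affected progressor's time to nadir off his result, and the median, if reached, no longer measures time from randomization, even when nadir timing is equal in the two arms. In the illustration, 12 months becomes 9 or 6. These sizes rest on assumed nadir times, assumed progression laws and complete 12-month follow-up; the actual size and direction in this trial are unknown. The effect on the between-arm test is a lesser matter: about 4–8% against a nominal 5% in the main scenarios with progressors only re-timed, and none when nadir timing is equal. The missing censoring rule matters because it leaves the treatment of non-progressors unstated. This is a secondary endpoint. The primary metabolic syndrome analysis, the sample size of 56 and time to radiographic progression are not affected by the sentence.

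**What to change.** In section 10.1.1, delete the sentence that contains "the PSA progression date is defined as the time from documented PSA nadir to an increase in PSA with confirmation as defined by protocol" and put in its place wording such as: *For every patient, time to PSA progression is measured from randomization to the progression date given by section 7.2.1. The nadir serves only as the reference value for the rise. Patients without PSA progression are censored at their last PSA assessment.*

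In sections 2.2 and 3.2, and in the Protocol Summary, which repeats their wording, point to the same definition. Leave section 7.2.1, including its use for stopping treatment, unchanged.

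The cost is one replaced passage and a few cross-references. No new data, visits or patients are needed.
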